4. LIST OF ABBREVIATIONS

The following abbreviations and specialist terms are used in this study protocol.

Abbreviations and Specialist Terms

Abbreviation or Specialist Term	Explanation
ADA	anti-drug antibody
ADAMTS13	a disintegrin and metalloproteinase with a thrombospondin type 1 motif, member 13
AE	adverse event
aHUS	atypical hemolytic uremic syndrome
ALT	alanine aminotransferase
AST	aspartate aminotransferase
AUC	area under time-concentration curve
BIW	twice weekly
BP	blood pressure
BTD	Breakthrough Therapy Designation
C3	Complement component 3
C3a	complement component 3a
C5a	complement component 5a
C5b-9	complement components 5b-9, also known as the membrane attack complex
CFH	complement factor H
CI	confidence interval
CL	clearance
C _{max}	maximum concentration
CRF	Case Report Form
CTCAE	Common Terminology Criteria for Adverse Events
DAH	diffuse alveolar hemorrhage
DMC	Data Monitoring Committee
ECG	electrocardiogram
EMA	European Medicines Agency
FAS	Full Analysis Set
FDA	Food and Drug Administration
GCP	Good Clinical Practice
GLP	Good Laboratory Practice
GVHD	graft-versus-host disease
Hgb	hemoglobin
HIPAA	Health Insurance and Portability and Accountability Act
HIV	human immunodeficiency virus
HSCT	hematopoietic stem cell transplant
HUS	hemolytic uremic syndrome
ICH	International Conference on Harmonisation
IgAN	immunoglobulin A nephropathy
IgG4	immunoglobulin G4
IEC	Independent Ethics Committee
IRB	Institutional Review Board

CONFIDENTIAL

No use, disclosure or reproduction outside of Omeros without prior written authorization

Abbreviation or Specialist Term	Explanation
IV	intravenous
λ_z	elimination rate constant
LDH	lactate dehydrogenase
LLN	lower limit of normal
LLOQ	lower limit of quantitation
mAb	monoclonal antibody
MASP	mannan-binding lectin-associated serine protease
MBL	mannan-binding lectin
MedRA	Medical Dictionary for Regulatory Activities
nM	nanomolar
NOAEL	no observed adverse effect level
OS	overall survival
PAS	Per-protocol Patient Set
PD	pharmacodynamic
PK	pharmacokinetic
QW	once weekly
RBC	red blood cell
RR	respiratory rate
RRT	renal replacement therapy
SAE	serious adverse event
SAP	statistical analysis plan
SC	subcutaneous
SOC	System Organ Class
STEC	Shiga toxin-producing E. coli
$t_{1/2}$	elimination half-life
TMA	thrombotic microangiopathy
TTP	thrombotic thrombocytopenic purpura
ULN	upper limit of normal
VOD	veno-occlusive disease

CONFIDENTIAL

5. INTRODUCTION

5.1. Background

This study was originally designed to provide preliminary information on the safety and potential efficacy of OMS721 for the treatment of thrombotic microangiopathies (TMAs). As originally designed, this study included 3 types of TMA—hematopoietic stem cell transplant-associated TMA (HSCT-TMA), atypical hemolytic uremic syndrome (aHUS), and thrombotic thrombocytopenic purpura (TTP)—and included 2 stages: a dose-escalation stage and a cohort expansion stage. A separate Phase 3 study has been initiated for patients with aHUS (Study OMS721-HUS-002); therefore, patients with aHUS are no longer being enrolled in Study OMS721-TMA-001. Patients with TTP are also no longer being enrolled in this study because it was difficult to observe a treatment effect over the current standard of care.

Improvements in laboratory TMA markers have been observed in patients with HSCT-TMA in this ongoing study, and marked unexpected improvements were observed in some patients with life-threatening disease. In support of an application for Breakthrough Therapy Designation (BTD) from the United States Food and Drug Administration (FDA), Omeros Corporation (Omeros, Sponsor) compared survival in OMS721-treated patients with a literature-based historical control. A substantial survival improvement was observed, and BTD was granted by FDA for the treatment of patients with HSCT-TMA who have persistent TMA despite modification of immunosuppressive therapy. The Sponsor has had continued discussions with regulatory agencies internationally regarding approval of OMS721 for the treatment of HSCT-TMA. These discussions have focused on approval based on patients with HSCT-TMA treated in this study as well as patients with HSCT-TMA treated under compassionate use or expanded-access protocols. Efficacy will be assessed by response to treatment evaluated by organ function or transfusion burden and laboratory measures of TMA.

Amendment 11 of this protocol provides for collection of additional data for OMS721-treated patients with HSCT-TMA to determine patient responses and longer-term outcomes and to support marketing authorization applications. The additional data to be collected are limited to patient demographics and baseline conditions, donor characteristics, the transplant procedure, concomitant medications, TMA-related laboratory measures, transfusions, transplant complications, and outcomes (see Section 19.4 for additional detail).

5.1.1. Description of OMS721

Omeros Corporation (Omeros, Sponsor) is developing OMS721, a human immunoglobulin G4 (IgG4) monoclonal antibody (mAb) to mannan-binding lectin-associated serine protease 2 (MASP-2), for the treatment of lectin complement pathway-mediated diseases.

The primary function of the complement system is to protect the host against infectious agents [Ricklin 2010]. This complex system targets immune and inflammatory responses to surfaces that display molecular patterns not usually present on healthy host cells. Activation of the complement system initiates a series of proteolytic steps that culminate in the formation of a membrane attack complex, which disrupts the membranes of targeted cells causing lysis and cell death. In addition, complement activation triggers opsonization and the recruitment of phagocytic cells to further engage the infectious agents.

CONFIDENTIAL

No use, disclosure or reproduction outside of Omeros without prior written authorization

Three pathways activate complement in response to distinct initiating events: the classical, lectin, and alternative pathways. The classical pathway is triggered by immune complexes and mediates important immune effector functions. The lectin pathway can be activated by specific types of cell-surface carbohydrate patterns that are usually found on microbes, but not on healthy host cell surfaces. These carbohydrate patterns are also found on injured host tissue. Lectin pathway activation is initiated by members of the MASP enzyme family. These proteases are synthesized as proenzymes that, in blood, form a complex with lectins, such as mannan-binding lectin (MBL), ficolins, and collectins. These lectins bind to carbohydrate patterns on foreign or injured host cell surfaces, targeting MASPs to their site(s) of action and leading to activation of MASPs. There are 3 known MASPs: MASP-1, MASP-2, and MASP-3 [Yongqing 2012]. MASP-2 is thought to be the key enzyme responsible for activation of the lectin pathway; upon activation, it cleaves its substrates, complement component 2 and complement component 4, both of which contribute to the formation of the complement component 3 (C3) convertase, which is a central component of complement activation.

OMS721 blocks the action of MASP-2, thereby inhibiting the lectin pathway of complement activation. The alternative pathway, by contrast, is continuously activated at a low level and is kept in check by a series of regulatory proteins. The alternative pathway also acts as an amplification loop, increasing the host immune response following activation of the classical and/or the lectin pathways. While the complement system supports innate host defense against pathogens, mutations in the genome or tissue damage can cause inappropriate activation and lead to serious disease, e.g., TMA, in which endothelial damage as well as fibrin and platelet-rich thrombi in the microvasculature lead to end-organ damage.

OMS721 is a fully human IgG4 mAb directed against MASP-2. OMS721 avidly binds to recombinant MASP-2 (apparent equilibrium dissociation constant approximately 100 picomolar) and exhibits greater than 5000-fold selectivity over the homologous proteins complement component 1s, complement component 1r, and MASP-1. In functional assays, OMS721 inhibits the human lectin pathway with nanomolar (nM) potency (concentration leading to 50% inhibition of approximately 3 nM) but has no significant effect on the classical or alternative complement pathways. OMS721 administered either by intravenous (IV) or subcutaneous (SC) injection to mice, non-human primates, and humans resulted in high plasma concentrations that were associated with suppression of lectin pathway activation in an *ex vivo* assay. OMS721 treatment reduced complement components 5b-9 (C5b-9, also known as the membrane attack complex) deposition and thrombus formation in *in vitro* models of TMA and inhibited thrombus formation in a mouse model of TMA, thus demonstrating that OMS721 is a potential candidate for the treatment of diseases that result from inappropriate lectin pathway activation.

5.1.2. Indication – Thrombotic Microangiopathies

Based on mechanism of action and results of nonclinical studies, OMS721 is in development for the treatment of TMA and other diseases potentially mediated by the lectin pathway of complement. Thrombotic microangiopathy is a descriptive name for histologic abnormalities consisting of thickening of arteriole and capillary walls with endothelial damage, subendothelial accumulation of protein and debris, and fibrin and platelet-rich thrombi occluding vessel lumina. The disorders that are associated with TMA are characterized by systemic or intrarenal aggregation of platelets, thrombocytopenia, and mechanical injury to erythrocytes.

CONFIDENTIAL

No use, disclosure or reproduction outside of Omeros without prior written authorization

Thrombotic microangiopathies may present as a primary condition or in association with other diseases. The classification scheme for TMA has evolved as the etiology and pathophysiology of distinct patient populations have been established [Besbas 2006]. Thrombotic microangiopathies can present with several clinical presentations, including TTP, aHUS, HSCT-TMA, and TMA caused by cancer chemotherapy, calcineurin inhibitor administration, and systemic lupus erythematosus.

5.1.2.1. Atypical Hemolytic Uremic Syndrome

Hemolytic uremic syndrome (HUS) occurs primarily in children following a diarrheal illness and is characterized by microangiopathic hemolytic anemia, thrombocytopenia, and acute renal failure. A major category of TMA is Shiga toxin-producing *Escherichia coli*-associated hemolytic uremic syndrome (STEC-HUS), which has also been referred to as diarrhea + HUS or typical HUS. Another type of HUS is atypical HUS (aHUS), which is a recurrent illness often associated with complement dysregulation.

Atypical HUS is a rare, life-threatening disease that, if left untreated, results in end-stage renal disease in 50% of patients within 1 year of diagnosis [Loirat 2011]. Dysregulation of the complement system is central to aHUS pathogenesis, and genetic abnormalities in complement genes have been identified in more than 60% of all aHUS patients. Certain mutant variants of the genes encoding complement factor H, factor I, factor B, and C3 have been identified as major risk factors; these alleles lead to increased complement activity. This complement hyperactivity is linked, by a mechanism that is not well understood, to a procoagulant phenotype on kidney endothelial cells that promotes the formation of microthrombi in the renal microvasculature and results in rapidly declining renal function in about half of affected individuals. Familial studies have shown that aHUS has incomplete penetrance and that approximately 50% of the carriers of the high-risk alleles develop the condition [Sullivan 2010]. It is thought that certain precipitating factors are needed to trigger aHUS. Such precipitating factors include infection, malignancies, use of endothelium-damaging drugs, transplantation, and pregnancy. Many of these precipitating factors are linked to endothelial cell activation, stress, or injury. Atypical HUS is treated with plasma therapy (plasma exchange or plasma infusion) or eculizumab, an anti-C5 mAb.

5.1.2.2. Thrombotic Thrombocytopenic Purpura

Thrombotic thrombocytopenic purpura was initially described as a syndrome that occurs primarily in adults characterized by a pentad of signs and symptoms consisting of thrombocytopenia, microangiopathic hemolytic anemia, neurologic and renal abnormalities, and fever. Thrombotic thrombocytopenic purpura is characterized by a severe deficiency of the von Willebrand factor-cleaving protease termed ADAMTS13 (a disintegrin and metalloproteinase with a thrombospondin type 1 motif, member 13).

In practice, the clinical distinction between TTP and HUS is not always clear [Moake 2002]. Thrombotic thrombocytopenic purpura has many of the same clinical and laboratory features as aHUS but is associated with low ADAMTS13 activity ($\leq 5\%$ to 10% of normal depending on the assay) due to genetic mutations or autoantibodies to the protein [George 2006]. It is typically associated with lower platelet counts, which can be severe. Plasma exchange is the standard treatment for TTP, with some patients requiring the addition of corticosteroids and/or rituximab to achieve an adequate response.

5.1.2.3. Hematopoietic Stem Cell Transplant-Associated Thrombotic Microangiopathy

Hematopoietic stem cell transplant-associated TMA is a serious multisystem disease affecting post-transplant outcomes [Jodele 2015]. The kidney is the most commonly affected organ, but the disease also occurs in the lung, central nervous system, gastrointestinal tract, and serosal tissues. The reported incidence of HSCT-TMA varies in retrospective and pathological reviews, but a prospective study of 100 pediatric patients found an incidence of 39%, 79% of which had features portending a poor prognosis [Jodele 2014a]. A recent large retrospective chart review of adult patients also reported an incidence of 39% [Postalcioglu 2018].

Hematopoietic stem cell transplantation induces substantial endothelial injury [Vion 2015]. This injury results from toxic conditioning regimens, immunosuppressive drugs, infections, and graft-versus-host disease (GVHD) [Khosla 2017]. This endothelial injury is believed to contribute to many serious post-HSCT complications, including veno-occlusive disease (VOD) (also known as sinusoidal obstructive syndrome), GVHD, capillary leak syndrome, diffuse alveolar hemorrhage (DAH), and TMA [Akil 2015, Carreras 2011, Khosla 2017, Vion 2015]. Preconditioning endothelial health and the degree of post-transplant endothelial injury measured by serum biomarkers are associated with both the development and severity of post-transplant complications [Cooke 2008, Dietrich 2013, Gloude 2017, Lindas 2014]. Suppression of tumorigenicity-2, a marker of endothelial injury, has been demonstrated to correlate with the risk of GVHD, TMA, and death following HSCT [Abu Zaid 2017, Rotz 2017a, Vander Lugt 2013]. The association of TMA and steroid-refractory GVHD has also been observed clinically and linked to endothelial injury [Rotz 2017a, Zeisbrich 2017]. Thus, TMA appears to be one manifestation of endothelial cell injury associated with HSCT. Limiting endothelial injury would be expected to reduce the severity of related clinical syndromes, such as TMA, as well as other complications related to endothelial cell injury.

Endothelial injury activates the lectin pathway of complement on the endothelial cell surface [Collard 2000]. Complement activation induces formation of complement component 3a (C3a) and complement component 5a (C5a). Preclinically, C3a and C5a have induced endothelial activation associated with endothelial injury and pro-inflammatory changes, leukocyte recruitment, and endothelial apoptosis [Mahajan 2016, Wu 2016, Zhang 2010]. Complement activation further leads to formation of C5b-9 on the cell surface. While membrane-bound, it can cause cell lysis. Even when sublytic, C5b-9 causes additional cell injury that induces secretion of prothrombotic factors, platelet activation, upregulation of adhesion molecules, and dysfunctional morphological changes in the endothelium [Kerr 2012]. These complement-mediated activities may amplify endothelial injury and dysfunction, causing or worsening clinical conditions.

Complement activation has been demonstrated in HSCT-TMA and GVHD [Cherry 2015, Rotz 2017b]. Eculizumab, a C5 inhibitor, has been reported to improve survival in patients with HSCT-TMA having features portending a poor prognosis [Bohl 2017, de Fontbrune 2015, Jodele 2014b]. Inhibition of the lectin pathway could limit endothelial cell injury by inhibiting both C3a and C5a, without increasing infection risk associated with classical pathway inhibition.

There are no approved products indicated for the treatment of HSCT-TMA. First-line management of HSCT-TMA includes modification or cessation of any immunosuppressive regimen, appropriate treatment of infections and/or GVHD if present, aggressive control of hypertension, and other supportive therapy as deemed appropriate by the treating physician

[Khosla 2017]. Plasma therapy is thought to have no utility in this patient population [Khosla 2017, Rosenthal 2016]. Patients who do not respond to modification of their immunosuppression have a poor prognosis. Adult mortality has been reported to be as high as 100% (4 out of 4 patients, all of whom died within 69 days from diagnosis) [Worel 2007]. In a larger and more recent series, only 17% of adult patients (4 out of 24) who underwent immunosuppression modification and received treatment with plasmapheresis, defibratide, or rituximab survived 1 year [Bohl 2017]. Eculizumab has been reported to treat HSCT-TMA effectively with a 90% response rate when used off-label in 1 adult study; however, there was a high rate of infection-related mortality following eculizumab treatment [Bohl 2017]. These data demonstrate that HSCT-TMA is a life-threatening condition and, with the lack of effective treatment options, represents a significant unmet medical need.

6. STUDY PURPOSE AND OBJECTIVES

The purpose of this Phase 2 study is to evaluate the safety, efficacy, PK, PD, and immunogenicity of OMS721 in patients with TMA. As of Amendment 11 of this study protocol, the primary and secondary endpoints are modified to provide for evaluation of response in patients with HSCT-associated TMA.

6.1. Primary Study Objectives

The co-primary objectives of this study are to:

- Assess the safety and tolerability of multiple-dose administration of OMS721 in patients with TMA (this will be assessed in patients with HSCT-TMA as well as in patients with aHUS or TTP)
- Evaluate the efficacy of OMS721 in patients with HSCT-TMA by response defined as:
 - Improvement in TMA laboratory markers of platelet count and lactate dehydrogenase (LDH), and
 - Improvement in clinical status

6.2. Secondary Study Objectives

The secondary objectives of this study are to evaluate the following in patients with HSCT-TMA treated with OMS721:

- Duration of response
- 100-day survival
- Overall survival (OS)
- Platelet count change from baseline
- Lactate dehydrogenase change from baseline
- Haptoglobin change from baseline
- Hemoglobin (Hgb) change from baseline
- Creatinine change from baseline in patients who had no reason other than HSCT-TMA for creatinine elevation
- Freedom from platelet transfusion in patients who received at least 1 platelet transfusion within 2 weeks of the first OMS721 dose
- Freedom from red blood cell (RBC) transfusion in patients who received at least 1 RBC transfusion within 2 weeks of the first OMS721 dose
- The PK of multiple-dose administration of OMS721 (this will be assessed in patients with HSCT-TMA as well as patients with aHUS and TTP)
- The PD of multiple-dose administration of OMS721 (this will be assessed in patients with HSCT-TMA as well as patients with aHUS and TTP)
- The immunogenicity of multiple-dose administration of OMS721 (this will be assessed in patients with HSCT-TMA as well as patients with aHUS and TTP)

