13.2.1.2. Analysis Populations

Efficacy analyses will be performed for the Full Analysis Set (FAS) population and the Per-protocol Patient Set (PAS) population. The FAS population will include all HSCT-TMA patients who received any amount of study drug. The PAS population will include all HSCT-TMA patients who received at least 4 weeks of study treatment (treatment period is ≥ 28 days).

Safety analyses will be based on the Safety Analysis Set population, which includes all patients (aHUS, TTP, and HSCT-TMA) who received any amount of study drug.

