 - Freedom from transfusion (no transfusions for at least 4 weeks from the last transfusion except for patients who died within 4 weeks of the last transfusion, only evaluated in patients who received transfusions within the 2 weeks prior to or on the first OMS721 dose date).

The secondary endpoints of this study are to evaluate the following in patients with HSCT-TMA treated with OMS721:

- Duration of response defined as the number of days from the first response date to the first relapse date
- 100-day survival, from the date of TMA diagnosis
- Overall survival, from the date of TMA diagnosis
- Freedom from platelet transfusion defined as no platelet transfusions for at least 4 weeks following the last platelet transfusion except for patients who died within 4 weeks of the last platelet transfusion (only evaluated in patients who had platelet transfusions in the 2 weeks prior to or on the first OMS721 dose date)
- Freedom from RBC transfusion defined as no RBC transfusions for at least 4 weeks following the last RBC transfusion except for patients who died within 4 weeks of the last RBC transfusion (only evaluated in patients who had RBC transfusions in the 2 weeks prior to or on the first OMS721 dose date)
- Change from baseline in platelet count (post-baseline platelet counts without platelet transfusions 2 days before and on the day of the platelet count collection will be used) over time using central laboratory values
- Change from baseline in LDH over time using central laboratory values
- Change from baseline in haptoglobin over time using central laboratory values
- Change from baseline in Hgb (post-baseline Hgb without RBC and whole blood transfusions 6 days before and on the day of the Hgb collection will be used) over time using central laboratory values
- Change from baseline in creatinine over time using central laboratory values

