2.8.2. Efficacy Analyses

2.8.2.1. Primary Efficacy Endpoint

A patient is a responder if this patient meets the responder criteria (Section 2.1) at any time post-baseline during the study. If a patient is not evaluable for a response criterion due to confounding factors, the non-evaluable response criterion will not be included in the determination of responder. Evaluability of each response criterion will be determined by a clinical review of relevant data and will be documented in the clinical study report. For example, potential confounding factors include graft failure for platelet count or transfusions, and nephrotoxic medications for renal function. Furthermore, laboratory values collected from both the local laboratories and the central laboratories will be used to determine response status.

Analysis of the primary efficacy endpoint will use a non-responder imputation to impute missing or incomplete data to evaluate response. The number and percent of responders will be summarized with exact 95% CI (Clopper-Pearson) by dose and total for the FAS and PAS

populations. If the lower bound of the exact 95% CI is greater than 15%, there is sufficient evidence to demonstrate efficacy of narsoplimab in the target patient population. Each criteria of the response will be listed for each patient.

Sensitivity analyses will include:

1. Subgroup analyses for the following subgroups will be performed for the FAS population:
 - Age (< 65 , ≥ 65 years)
 - Gender (Male or Female)
 - Graft-versus-host disease (GVHD) (Yes or No)
 - Significant infection (Yes or No)
 - Graft failure or non-engraftment (Yes or No)
 - Female-to-male transplant (Yes or No)
 - Multiple organ TMA involvement (Yes or No)
 - Mismatched donor (Yes or No)
 - Baseline platelet counts ($< 20,000$ or $\geq 20,000$ platelets/ μL)
 - Renal dysfunction at baseline (Creatinine $> \text{ULN}$ or spot urine protein $\geq 2+$ or > 30 mg/dL; Yes or No)
 - Any transfusions within the 2 weeks prior to or on the first OMS721 dose date (Yes or No)
2. A completer analysis will be performed using the patients with non-missing responses only. Exact 95% CI for the completer response rate will be provided for the FAS population by dose.
3. Two alternative definitions of response will be analyzed:

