2.8.2.2.4. Other Secondary Endpoints

Binary secondary efficacy endpoints will be summarized with exact 95% CI by dose for the FAS population. Non-responder imputation will be used to handle missing data.

For each of the continuous secondary efficacy endpoints, 2 analyses will be performed by dose for the FAS population:

1. A time-weighted average analysis will be performed. The time-weighted average of the change from baseline is defined as the area-under-the-curve (AUC) of the change from baseline divided by the observation time over the study period. The AUC of the change from baseline is calculated by the trapezoidal rule using all observed change from baseline data. Summary statistics and 95% CI for the mean time-weighted average will be provided. One-sample t-test will also be performed.

2. A repeated measures model with the baseline value of the endpoint and time as fixed effects will be used to estimate the mean change from baseline over time. Time will be defined as a categorical variable in weeks according to the scheduled visits (Section 2.6). A generalized estimating equation approach with an autoregression (AR(1)) working correlation structure will initially be used to estimate the model parameters. If estimation of this model fails due to any reason, alternative model specifications (e.g., linear, quadratic, or log-scale time trends) will be considered by examination of the data. The least squares mean change from baseline will be estimated with 95% CI for each time point.

In addition, efficacy laboratory values of platelet count, LDH, creatinine, hemoglobin and haptoglobin will be plotted over time for the HSCT-TMA patients.

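### The creatinine objective is limited to patients with no other cause of raised creatinine, but every planned creatinine analysis uses the whole FAS, so the stated objective goes unanswered

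*Protocol*

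**What the plan says.** The objective, in protocol 6.2 and again in SAP 1.1, is "Creatinine change from baseline in patients who had no reason other than HSCT-TMA for creatinine elevation".

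The endpoint that should serve it is "Change from baseline in creatinine over time using central laboratory values" (SAP 2.1; the protocol synopsis and protocol 7.3.2 agree). It says nothing about the cause of the elevation.

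On analysis, SAP 2.8.2.2.4 states: "For each of the continuous secondary efficacy endpoints, 2 analyses will be performed by dose for the FAS population". The first is described as "A time-weighted average analysis will be performed", with a 95% CI for the mean and a one-sample t-test. The second is "A repeated measures model with the baseline value of the endpoint and time as fixed effects will be used", fitted by generalized estimating equations. On the population, protocol 13.2.1.2 says: "The FAS population will include all HSCT-TMA patients who received any amount of study drug".

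The one place that deals with competing renal causes is the primary endpoint. SAP 2.8.2.1 provides for a clinical review of whether each response criterion is evaluable and gives "nephrotoxic medications for renal function" as an example of confounding.

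**The concern.** The objective asks about creatinine in patients whose elevation has no explanation apart from HSCT-TMA. The planned analyses ask about creatinine in everyone treated. These questions differ whenever some patients have another cause and their creatinine follows a different course.

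The trial has no control arm, so choosing the population is one of the few ways the plan can keep other influences on creatinine out of the estimate. The interim report is meant to support a marketing submission (protocol 13.2.10, SAP 2.8.5). As the plan stands, a FAS mean and its t-test could be presented under an objective that they do not address.

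**Working it through.** **1. The plan's own figure.** The only sample-size figure concerns the response rate. Clopper-Pearson intervals for 0 to 28 responders out of 28 have widths from 12.3% to 38.7%, and 14/28 gives 30.6% to 69.4%. Both match protocol 13.1 and SAP 1.3. Nothing is stated for creatinine, and this point changes none of these figures. The HSCT-TMA column of SAP Table 1 sums to 2 + 22 + 4 = 28, of whom 4 are at 370 mg.

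**2. Does anything elsewhere supply the restriction?**

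- *Endpoint text:* no, in all three places. The neighbouring platelet and RBC transfusion objectives are also restricted, and their restriction is carried into the endpoint. Among these three restricted objectives, only creatinine loses it.
- *Eligibility (protocol 8.1):* no. Criterion 5 rules out other explanations for low platelets and anemia, not for raised creatinine. The renal criterion is a doubling of creatinine from the pre-transplant value, with no cause required.
- *Evaluability review (SAP 2.8.2.1):* no. It decides which criteria count towards responder status and does not reach the continuous endpoints.
- *Renal-dysfunction subgroup (SAP 2.8.2.1):* no. It belongs to the primary endpoint and is defined by level of creatinine or urine protein, not cause.
- *Stratified repeat (SAP 2.8.2.2.5):* no. It splits by responder status.
- *Repeated-measures model:* no. Its fixed effects are baseline and time only.

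The redacted SAP 2.8.3 is the section that SAP 3.3 cites for PK, PD and immunogenicity, so redaction does not explain the gap.

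**3. Direction and size.** Let q be the share of the FAS with another cause, M_R the mean change in the objective's population and M_O the mean change in the others. For a simple mean, such as the mean time-weighted average:

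M_FAS = (1 − q)·M_R + q·M_O, so M_FAS − M_R = q·(M_O − M_R).

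The documents give none of q, M_R or M_O. Purely as assumptions, take a fall of 10 units in the objective's population:

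| Assumed course in the others | q = 0.10 | q = 0.50 |
|---|---|---|
| Fall of 40 units | 0.9×10 + 0.1×40 = 13 | 0.5×10 + 0.5×40 = 25 |
| Fall of 10 units | 10 | 10 |
| No change | 0.9×10 + 0.1×0 = 9 | 0.5×10 + 0.5×0 = 5 |

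The FAS mean may overstate, match or understate the mean that the objective asks for.

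**4. Precision of a restricted analysis.** The 95% CI half-width for a mean, in SD units, is t(0.975, m − 1)/√m. Subset sizes below 28 are assumed.

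- m = 28: 2.052/5.292 = 0.39 SD
- m = 21: 2.086/4.583 = 0.46 SD (1.17 times)
- m = 14: 2.160/3.742 = 0.58 SD (1.49 times)

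**The case against.** The strongest reply is that this is a wording inconsistency on one of many secondary endpoints. The endpoint is unrestricted wherever it is defined, summaries are called descriptive (SAP 3.1), there is no multiplicity adjustment (SAP 2.8.1), and the only efficacy threshold belongs to the primary endpoint, where renal confounding is addressed. The documents do not show which text reflects the sponsor's intent. This limits the consequence and makes correcting the objective a legitimate alternative. It does not make the objective answered.

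A second reply is that restriction can do harm. The study is unblinded and enrollment is complete, so a clinical review that sees post-baseline creatinine could select patients by outcome. The FAS avoids that. This stands, and it determines how the set must be built. With only 4 patients at 370 mg, a by-dose restricted analysis may also be unworkable.

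Three stronger readings are tempting, and the documents do not support them.

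- A reader might infer that the evaluability review already flags the right patients. Being non-evaluable for the renal criterion is a different condition from having another cause of elevation: that criterion also includes stopping renal replacement therapy, and confounding may arise after baseline.
- A reader might infer that the restriction would remove the influence of dialysis. Dialysis does not cause creatinine elevation, and a patient dialysed because of HSCT-TMA stays in the restricted set.
- A reader might infer that the FAS analysis inflates the apparent drug effect. The sign depends on how the other patients fare, which is unknown.

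**Conclusion.** The point holds as a mismatch between objective and analysis. Two documents state a restricted objective, three endpoint definitions omit the restriction, and both planned analyses use all treated HSCT-TMA patients. Following the plan exactly would leave a stated secondary objective without an estimate.

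The gap between the two populations is q·(M_O − M_R), of unknown sign and size; the values in the table are assumptions. The finding does not touch the primary endpoint or any stated figure. Nor would a restricted analysis allow a creatinine change to be attributed to OMS721 in a trial without a control. It would only answer the question the objective asks. The matter should be settled before interim database lock, the point by which protocol 13.2 requires the SAP to be final.

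**What to change.** In SAP 2.8.2.2.4:

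1. Define the restricted set by explicit criteria using information up to the first dose, for example recorded nephrotoxic medications or other documented renal causes. State how patients without a raised creatinine at that time are classed, and who applies the criteria. The evaluability review may inform this but should not stand in for it.
2. Fix membership before interim database lock, without reference to post-baseline creatinine.
3. Run the time-weighted average and repeated-measures creatinine analyses in that set alongside the FAS analyses. Combine doses if the 370 mg group is too small; protocol 13.2.1 already provides for a combined-dose summary.
4. Carry the restriction into the endpoint wording in the protocol synopsis, protocol 7.3.2 and SAP 2.1, as is done for the transfusion endpoints.

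If the sponsor does not intend the restriction, remove it from protocol 6.2 and SAP 1.1, so that the FAS result is not reported as answering a narrower objective.

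The cost is one more population for one secondary endpoint, the work of classifying about 28 patients, and the loss of precision shown above. Relevant inputs are already collected with dates under protocol 19.4, including kidney diagnoses, immunosuppressives and anti-infectives.
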